## 9.10 Subgroup Analyses

To determine whether the treatment effect is consistent across various subgroups, the estimate of the between-group treatment effect (with a nominal 95% CI) for the primary endpoint will be estimated and plotted within each category of each subgroup. The following are examples of classification variables:

- Age ( $\leq 60$  years,  $> 60$  years)
- Sex (female, male)
- Race (American Indian or Alaska Native, Asian, Black or African American, Native Hawaiian or Other Pacific Islander, White)
- Time from symptom onset prior to the day of randomization ( $\leq 5$  days,  $> 5$  days)
- Baseline (Day 1) disease severity (mild, moderate, severe) per Appendix 9
- Remdesivir use prior to or at the time of randomization (yes, no)
- Corticosteroid use prior to or at the time of randomization (yes, no)
- Geographic region (North America, Europe, Asia Pacific, Latin America)

- Participants at increased risk for severe illness from COVID-19 (yes, no)
  - age >60 years, active cancer, chronic kidney disease, chronic obstructive pulmonary disease, immunocompromised state from solid organ transplant, obesity (BMI  $\geq 30$ ), serious heart conditions such as heart failure, coronary artery disease, or cardiomyopathies, sickle cell disease, diabetes mellitus

Additional subgroups may be defined in the sSAP. Categories of the above subgroups with small sample sizes (<25 per treatment group) may be combined – further detail will be provided in the sSAP.

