#### **4.2.4 Rationale for Collection of Racial, Ethnic, and Gender Identity Data**

The differential effect on the safety and efficacy based on any demographic parameter, including race, ethnicity, or gender identity, cannot be predicted when evaluating a new investigational drug. Therefore, it is important to collect race, ethnicity and gender identity data to ensure that there is not a differential effect based on these parameters. These data will also provide assurance that the results observed in the clinical study will be representative of the drug's use in a broader patient population, including transgender people whose gender identities and/or expressions differ from the sex assigned to them at birth. Also, subgroup analyses on race and ethnicity will be performed to better understand how these parameters may influence clinical outcome and toxicity.

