#### **6.3.2 Stratification**

Intervention randomization will be stratified according to the following factors:

1. Time from symptom onset prior to the day of randomization ( $\leq 5$  days,  $>5$  days)
2. Age ( $\leq 60$  years,  $>60$  years)
3. Remdesivir use for treatment of the index diagnosis of COVID-19 prior to or at the time of randomization (yes, no)

Based on the viral kinetics of SARS-CoV-2 and the mechanism of action of MK-4482, treatment with antiviral therapy is likely to have a greater benefit with early treatment ( $\leq 5$  days) rather than late treatment ( $>5$  days). Older age is also associated with more severe outcomes, and the WHO notes that people older than 60 years are at higher risk for severe illness due to COVID-19. Finally, remdesivir has been demonstrated to shorten the time to recovery in hospitalized patients with COVID-19 and may be used concurrently in this study. The selection of these criteria as stratification factors will help ensure that the treatment groups will be well balanced within each stratum and the study results will not be confounded by factors suspected to have a potential impact on a participant's response to study intervention.

Of note, enrollment of participants with severe COVID-19 (Appendix 9) will be limited to 50% of the total planned sample size in both Parts 1 and 2.

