## 9.9 Sample Size and Power Calculations

### 9.9.1 Sample Size and Power Calculations for Efficacy Analyses (Part 2)

The primary analysis of Phase 3 study endpoints will include ~1000 participants from Part 2 of the study (~500 for the selected MK-4482 group and ~500 for the placebo group) who meet the criteria for inclusion in the MITT population. The primary endpoint is time-to-sustained recovery. The study has overall power of 90% to demonstrate that participants treated with MK-4482 have a higher rate of sustained recovery than participants treated with placebo at an overall one-sided, 2.5% alpha-level, if the underlying constant sustained recovery rate ratio between treatment groups is 1.3.

The power and sample size are based on the following assumptions: 1) the time-to-sustained recovery follows an exponential distribution with sustained recovery rates of 0.351 and 0.270 for the MK-4482 and placebo groups, respectively, 2) a futility/efficacy interim analysis at 50% information as outlined in Section 9.7, 3) an enrollment period of 10 weeks, and 4) dropout hazard rates of 0.02 for both the MK-4482 and placebo groups, respectively. The above sustained recovery rates correspond to approximately 366 (73%) and 319 (64%) sustained recovery events for the MK-4482 and placebo groups, respectively. These are nearly identical to the recovery rates presented for remdesivir and placebo in the NEJM [Beigel, J. H., et al 2020]. The calculation was computed using both EAST and gsDesign. To meet the statistical criterion for success (one-sided p value $\leq$ 0.019 at the final analysis), the observed sustained recovery rate ratio must be approximately 1.17 or larger.

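### Section 9.10 aims to determine whether the treatment effect is consistent across subgroups, but plans no between-subgroup contrast, not even for symptom onset, where Section 6.3.2 predicts a difference

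*Combined protocol and SAP*

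**What the plan says.** Section 9.10 states its aim and its method in one sentence. It begins "To determine whether the treatment effect is consistent across various subgroups, the estimate of the between-group treatment effect (with a nominal 95% CI", and goes on to say that this estimate, for the primary endpoint, "will be estimated and plotted within each category of each subgroup". Nine classification variables follow, introduced as examples. Six have two categories, severity has three, region four and race five.

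Neither Section 9.10 nor any other section mentions a treatment-by-subgroup term, a heterogeneity test, a ratio of rate ratios, or a rule for reading the plot. Section 9.10 refers to the supplemental SAP (sSAP) for two things only: "Additional subgroups may be defined in the sSAP", and the pooling of categories with fewer than 25 participants per group.

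Two other sections bear on the question. Section 6.3.2 explains why symptom onset is a stratification factor: "treatment with antiviral therapy is likely to have a greater benefit with early treatment", meaning within 5 days rather than later. Section 4.2.4 says that "it is important to collect race, ethnicity and gender identity data to ensure that there is not a differential effect based on these parameters".

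**The concern.** The stated question is whether the effect differs between categories. The planned output is a set of within-category effects, so the reader must make the comparison by eye. Two informal rules are common, and they err in opposite directions. Noting which intervals exclude 1 confuses a loss of precision with a loss of effect. Requiring the intervals not to overlap is much stricter than a 5% test of the difference.

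The risk is one of interpretation. Benefit could be described as confined to one category when the effect is the same in both. Equally, a real difference by symptom onset, the one factor for which the protocol predicts a direction, could be passed over because no contrast was specified before unblinding.

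**Working it through.** **Inputs from the documents.** Total events 685, with the interim at about 343 (Section 9.7). Section 9.9.1 gives power "at an overall one-sided, 2.5% alpha-level" and "if the underlying constant sustained recovery rate ratio between treatment groups is 1.3". Allocation is 1:1 (Section 4.1). The spending function is Gamma with parameter −1 (Section 9.7).

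**Assumptions.** Events are Part 2 events and divide in proportion to subgroup size. Subgroup shares are not given, except that severe disease is capped at 50% (Section 6.3.2), so splits from 50/50 to 20/80 are shown.

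**Step 1: reproduce the plan's own figures.** With SE(log ratio) = 2/√events, the interim and final critical values are 2.348 and 2.066.
- Interim efficacy ratio: exp(2 × 2.348/√343) = 1.289 (stated 1.289).
- Final ratio: exp(2 × 2.066/√685) = 1.171 (stated about 1.17).
- Power: 90.4% counting the futility bound (stated 90%).

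The same SE formula can therefore be used within subgroups.

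**Step 2: reading each interval by whether it excludes 1, with a true ratio of 1.3 in every category.** For a category with e events, p = Φ(ln 1.3 × √e/2 − 1.96). For two categories, P(exactly one excludes 1) = p₁(1 − p₂) + p₂(1 − p₁).

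| Event split | e₁, e₂ | p₁, p₂ | Exactly one excludes 1 |
|---|---|---|---|
| 50/50 | 342.5, 342.5 | 0.680, 0.680 | 43.5% |
| 30/70 | 205.5, 479.5 | 0.468, 0.819 | 52.0% |
| 20/80 | 137, 548 | 0.336, 0.867 | 62.1% |

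Among simulated trials that succeed overall, the figures are 45%, 54% and 65%. For more than two categories, the chance of a mixed picture is 1 − Πp − Π(1 − p): 75% for three equal categories, 85% for four equal categories, and 89% for five with assumed shares of 50/20/15/10/5%. An interaction test at two-sided 0.05 falsely signals 5% of the time per factor.

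**Step 3: reading by non-overlap.** Two intervals fail to overlap when |difference| > 1.96(SE₁ + SE₂). The equivalent threshold is z = 1.96(SE₁ + SE₂)/√(SE₁² + SE₂²).
- 50/50: z = 1.96 × √2 = 2.77, two-sided error 0.6%.
- 20/80: SEs are 0.171 and 0.085, so z = 2.63 and the error is 0.9%.

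**Step 4: power when a difference is real.** Take assumed ratios of 1.6 (≤5 days) and 1.05 (>5 days) at 50/50. The SE of the difference in log ratios is √(4/342.5 + 4/342.5) = 0.1528, and ln(1.6/1.05) = 0.421, so the expected z is 2.76.
- Interaction test: Φ(2.76 − 1.96) = 79%.
- Non-overlap: Φ(2.76 − 2.77) = 49%.

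At 30/70 the two figures are 71% and 43%. The interaction test falls to 60% at 20/80. At 50/50 its power is 41% for 1.5 versus 1.15, and 17% for 1.4 versus 1.2.

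**Step 5: limits of the contrast.** The ratio of rate ratios detectable with 80% power is exp(2.80 × SE): 1.53 at 50/50, 1.60 at 30/70 and 1.71 at 20/80. Nine independent unadjusted tests give 1 − 0.95⁹ = 37% chance of at least one false signal.

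**The case against.** Four points on the other side carry weight.

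- **Nothing confirmatory rests on Section 9.10.** Section 3 has no subgroup hypothesis, Section 9.8 confines error control to the primary endpoint and mortality, and the intervals are labelled nominal. Section 6.3.2 gives its expectation about early treatment as a reason to stratify and does not state an interaction hypothesis. All of this stands, and it limits the importance of the point.
- **The 44% to 62% figures measure a reading rule that the plan does not contain.** This also stands. They show how one common reading behaves and say nothing about what the sponsor intends.
- **An interaction test is weak here, and nine of them raise multiplicity.** Correct, as Steps 4 and 5 show. It is a reason to report the contrast with its interval and say plainly what it cannot show. It does not favour leaving the comparison to the eye.
- **The sSAP could add the contrast.** The opening of Section 9 allows non-confirmatory changes there before unblinding, but nothing in the documents says that this will be done.

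A reader might go further and infer that the planned output cannot address consistency, or that a difference by symptom onset would have no estimate. The documents do not support that. Both onset categories are listed, so both rate ratios and intervals will be reported. The categories share no participants, so the difference and its SE, √(SE₁² + SE₂²), can be derived from the planned output. What is missing is a specified and reported contrast. A reader might also infer that a false single-subgroup finding is likely for at least one of the nine factors. That again assumes the exclude-1 rule, and the factors overlap (age over 60 is part of the risk-status factor), so the per-factor figures cannot simply be combined.

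**Conclusion.** The point holds as a matter of analysis and reporting. Section 9.10 sets an inferential aim, plans only within-category estimates, and never specifies the contrast that addresses the aim, including for the one factor where the protocol predicts a direction.

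With the plan's 685 events and a common true ratio of 1.3, judging two intervals by whether each excludes 1 misleads 44% to 62% of the time. For a common ratio of 1.17 to 1.25 the range is 42% to 62%. Judging by non-overlap rarely misleads in that direction, but gives up substantial power (49% against 79% in the assumed 1.6 versus 1.05 case). These sizes depend on the reading rule, the event splits and the assumed ratios, none of which the plan states. The primary test, its boundaries and its power are unaffected.

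**What to change.** Add to Section 9.10:

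- For each factor, fit the planned stratified Cox model with a treatment-by-subgroup interaction. Include the subgroup main effect for the six factors that are not randomisation strata (sex, race, severity, corticosteroid use, region, risk status).
- For two-category factors, report the ratio of rate ratios with its 95% CI and nominal p-value. For severity, region and race, report a global heterogeneity test (2, 3 and 4 degrees of freedom before any pooling of small categories). Place these beside the forest plot.
- Name symptom onset (≤5 versus >5 days) as the one pre-stated interaction of interest. Label the rest descriptive and unadjusted.
- State the limits: 80% power needs a ratio of rate ratios of about 1.53 even at a 50/50 split, a non-significant result does not establish consistency, and nine unadjusted tests carry about a 37% chance of at least one false signal if independent.

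The cost is a short paragraph and a few extra model terms, with no new data, visits or participants. If the sponsor prefers to keep the section descriptive, the minimum is to reword its aim accordingly and still prespecify the symptom-onset contrast.

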### **9.11 Compliance (Medication Adherence)**

Compliance will be calculated based on capsule counts. For a participant who is followed for the entire study period, the “Number of Capsules Should be Taken” is the total number of capsules should be taken from randomization to the last scheduled day for treatment administration for that participant. For a participant who discontinues from the study permanently, the “Number of Capsules Should be Taken” is the total number of capsules should be taken from randomization to the date of the last dose of study intervention. The “Number of Capsules Taken” will be based on data reported in the eCRF.

For each participant, percent compliance will then be calculated using the following formula:

$$\text{Percent Compliance} = \frac{\text{Number of Capsules Taken}}{\text{Number of Capsules Should be Taken}} \times 100$$

Summary statistics will be provided on percent compliance by treatment group for the MITT population.

### **9.12 Extent of Exposure**

The Extent of Exposure to study treatment will be evaluated by summary statistics (N, mean, median, standard deviation) for the “Number of Capsules Taken” by treatment group.

## 10 SUPPORTING DOCUMENTATION AND OPERATIONAL CONSIDERATIONS

### 10.1 Appendix 1: Regulatory, Ethical, and Study Oversight Considerations

#### 10.1.1 Code of Conduct for Clinical Trials

Merck Sharp and Dohme Corp., a subsidiary of Merck & Co., Inc. (MSD)

#### Code of Conduct for Interventional Clinical Trials

##### I. Introduction

###### A. Purpose

MSD, through its subsidiaries, conducts clinical trials worldwide to evaluate the safety and effectiveness of our products. As such, we are committed to designing, implementing, conducting, analyzing, and reporting these trials in compliance with the highest ethical and scientific standards. Protection of participants in clinical trials is the overriding concern in the design and conduct of clinical trials. In all cases, MSD clinical trials will be conducted in compliance with local and/or national regulations (including all applicable data protection laws and regulations), and International Council for Harmonisation Good Clinical Practice (ICH-GCP), and also in accordance with the ethical principles that have their origin in the Declaration of Helsinki.

###### B. Scope

Highest ethical and scientific standards shall be endorsed for all clinical interventional investigations sponsored by MSD irrespective of the party (parties) employed for their execution (e.g., contract research organizations, collaborative research efforts). This Code is not intended to apply to trials that are observational in nature, or which are retrospective. Further, this Code does not apply to investigator-initiated trials, which are not under the full control of MSD.

##### II. Scientific Issues

###### A. Trial Conduct

###### 1. Trial Design

Except for pilot or estimation trials, clinical trial protocols will be hypothesis-driven to assess safety, efficacy and/or pharmacokinetic or pharmacodynamic indices of MSD or comparator products. Alternatively, MSD may conduct outcomes research trials, trials to assess or validate various endpoint measures, or trials to determine patient preferences, etc.

The design (i.e., participant population, duration, statistical power) must be adequate to address the specific purpose of the trial and shall respect the data protection rights of all participants, trial site staff and, where applicable, third parties. Participants must meet protocol entry criteria to be enrolled in the trial.

###### 2. Site Selection

MSD selects investigative sites based on medical expertise, access to appropriate participants, adequacy of facilities and staff, previous performance in clinical trials, as well as budgetary considerations. Prior to trial initiation, sites are evaluated by MSD personnel (or individuals acting on behalf of MSD) to assess the ability to successfully conduct the trial.

###### 3. Site Monitoring/Scientific Integrity

Investigative trial sites are monitored to assess compliance with the trial protocol and Good Clinical Practice (GCP). MSD reviews clinical data for accuracy, completeness, and consistency. Data are verified versus

source documentation according to standard operating procedures. Per MSD policies and procedures, if potential fraud, scientific/research misconduct, privacy incidents/breaches or Clinical Trial-related Significant Quality Issues are reported, such matters are investigated. When necessary, appropriate corrective and/or preventative actions are defined and regulatory authorities and/or ethics review committees are notified.

#### **B. Publication and Authorship**

Regardless of trial outcome, MSD commits to publish the primary and secondary results of its registered trials of marketed products in which treatment is assigned, according to the pre-specified plans for data analysis. To the extent scientifically appropriate, MSD seeks to publish the results of other analyses it conducts that are important to patients, physicians, and payers. Some early phase or pilot trials are intended to be hypothesis-generating rather than hypothesis testing; in such cases, publication of results may not be appropriate since the trial may be underpowered and the analyses complicated by statistical issues such as multiplicity.

MSD's policy on authorship is consistent with the recommendations published by the International Committee of Medical Journal Editors (ICMJE). In summary, authorship should reflect significant contribution to the design and conduct of the trial, performance or interpretation of the analysis, and/or writing of the manuscript. All named authors must be able to defend the trial results and conclusions. MSD funding of a trial will be acknowledged in publications.

### **III. Participant Protection**

#### **A. Regulatory Authority and Ethics Committee Review (Institutional Review Board [IRB]/Independent Ethics Committee [IEC])**

All protocols and protocol amendments will be submitted by MSD for regulatory authority acceptance/authorization prior to implementation of the trial or amendment, in compliance with local and/or national regulations.

The protocol, protocol amendment(s), informed consent form, investigator's brochure, and other relevant trial documents must be reviewed and approved by an IRB/IEC before being implemented at each site, in compliance with local and/or national regulations. Changes to the protocol that are required urgently to eliminate an immediate hazard and to protect participant safety may be enacted in anticipation of ethics committee approval. MSD will inform regulatory authorities of such new measures to protect participant safety, in compliance with local and/or national regulations.

#### **B. Safety**

The guiding principle in decision-making in clinical trials is that participant welfare is of primary importance. Potential participants will be informed of the risks and benefits of, as well as alternatives to, trial participation. At a minimum, trial designs will take into account the local standard of care.

All participation in MSD clinical trials is voluntary. Participants enter the trial only after informed consent is obtained. Participants may withdraw from an MSD trial at any time, without any influence on their access to, or receipt of, medical care that may otherwise be available to them.

#### **C. Confidentiality**

MSD is committed to safeguarding participant confidentiality, to the greatest extent possible, as well as all applicable data protection rights. Unless required by law, only the investigator, Sponsor (or individuals acting on behalf of MSD), ethics committee, and/or regulatory authorities will have access to confidential medical records that might identify the participant by name.

#### **D. Genomic Research**

Genomic research will only be conducted in accordance with a protocol and informed consent authorized by an ethics committee.

#### **IV. Financial Considerations**

##### **A. Payments to Investigators**

Clinical trials are time- and labor-intensive. It is MSD's policy to compensate investigators (or the sponsoring institution) in a fair manner for the work performed in support of MSD trials. MSD does not pay incentives to enroll participants in its trials. However, when enrollment is particularly challenging, additional payments may be made to compensate for the time spent in extra recruiting efforts.

MSD does not pay for participant referrals. However, MSD may compensate referring physicians for time spent on chart review and medical evaluation to identify potentially eligible participants.

##### **B. Clinical Research Funding**

Informed consent forms will disclose that the trial is sponsored by MSD, and that the investigator or sponsoring institution is being paid or provided a grant for performing the trial. However, the local ethics committee may wish to alter the wording of the disclosure statement to be consistent with financial practices at that institution. As noted above, all publications resulting from MSD trials will indicate MSD as a source of funding.

##### **C. Funding for Travel and Other Requests**

Funding of travel by investigators and support staff (e.g., to scientific meetings, investigator meetings, etc.) will be consistent with local guidelines and practices.

#### **V. Investigator Commitment**

Investigators will be expected to review MSD's Code of Conduct as an appendix to the trial protocol, and in signing the protocol, agree to support these ethical and scientific standards.

